## **7.2. Radiographic Procedures/Evaluations**

### **7.2.1. Esophagoscopy**

The patient will present for endoscopic evaluation the day prior to surgery. During this time the patient will undergo moderate sedation with continual monitoring of vital signs. Following adequate sedation the proceduralist will proceed with esophageal intubation with visual assessment of the entire esophagus and grading of lesions (Zargar classification). Furthermore, the submucosal tissue will be assessed with EUS at the level of the left atrium. This procedure will be preceded by TEE with moderate sedation maintained.

The day following the PVI the patient will undergo repeat endoscopic evaluation of the esophagus in the same manner as detailed above. The proceduralist will document their findings including the condition of the sub-mucosal esophageal tissue as noted by EUS.

## **7.3. Study Schedule**

### **7.3.1. Screening/Enrollment/Baseline (Visit 1, Day 0)**

#### **Screening/Enrollment/Baseline Visit (Visit 1)**

- Obtain informed consent of potential participant verified by signature on written informed consent form
- Review medical history to determine history based on inclusion/exclusion criteria
- Review medications history to determine eligibility based on inclusion/exclusion criteria
- Obtain demographic information and tobacco use history

- Record vital signs, results of examinations, other assessments
- Perform medical examinations needed to determine eligibility based on inclusion/exclusion criteria
- Schedule EGD 1 day prior to surgery.
- Schedule follow-up visits for patients who are eligible and available for the duration of the study
- Provide patients with instructions needed to prepare for the first study visit/procedure

### **7.3.2. Endoscopic evaluation and TEE (Visit 2)**

The patient will present to the hospital on the day prior to their RF ablation procedure as is standard of care for transesophageal echocardiography (TEE). The patient will be prepped for moderate conscious sedation with appropriate monitoring of vital signs under the care of a nurse and as directed by the physician. For this study we will add the patient will undergo direct visualization of the esophageal mucosa as well as ultrasound assessment of the sub-mucosal tissue in the area of the left atrium. The patient will be sedated to a level of moderate conscious sedation as is typical for endoscopic evaluation and TEE. The endoscopic probe will be passed into the esophagus with appropriate imaging obtained throughout the length of the esophagus. Then EUS will be used to assess the submucosal tissue

### **7.3.3. Surgical Procedure Visit (Visit 3)**

Subjects will undergo the RF ablation procedure within 30 days of randomization unless there is a medically valid reason to delay the procedure. The procedure is described below. Details of the procedure are referenced in section 7.1.2 of this study protocol. The investigator's procedure note will be included in the study files to gather endpoint and exploratory data.

The following day the patient will undergo repeat endoscopic evaluation in the same fashion as the prior study with moderate sedation. This will include visual assessment of the esophagus with video imaging as well as EUS at the area of interest near the left atrium at the level of the pulmonary veins.

### **7.3.4. Follow-up Visit (Visit 3)**

The first follow-up visit will occur 12 days (+4/-4) days after the surgery procedure.

- Review medical history and medications history
- Record vital signs
- Adverse event assessment
- Assess study eligibility

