### **5.2. Exclusion Criteria**

- Subject has known esophageal deformity, or evidence of esophageal trauma, prior radiation therapy involving the esophagus, or previous esophageal disease (for example, known esophageal varices, cirrhosis, history of esophagectomy, previous swallowing disorders or dysphagia, achalasia, known ingestion of acidic or caustic poisons within the prior 24 hours etc.).
- Subject is incarcerated
- Subject is pregnant or plans to become pregnant
- Subject has a silicone allergy
- Subject has esophageal bleeding prior to EnsoETM insertion

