### **7.3.5. Final Study Visit (Visit 4)**

The final study visit will occur 3 months (+30/-30 days) after the surgery procedure.

- Review medical history and medications history
- Record vital signs
- Adverse event assessment
- PVI Efficacy as assessed through placement of an event monitor
- Assess study eligibility

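### No eligibility recheck is scheduled between Visit 1 and ablation; the check is listed instead at day 12 and 3 months, when one exclusion criterion can coincide with the study outcome

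*Protocol*

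**What the plan says.** Sections 7.3.3 and 7.3.4 of the Protocol both carry the label Visit 3, so section numbers are used here.

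- **7.3.1 (Visit 1, Day 0)** holds the eligibility work: review of history and medications against the criteria, and "Perform medical examinations needed to determine eligibility based on inclusion/exclusion criteria".
- **7.3.2 (Visit 2, the day before ablation)** covers TEE, endoscopy and endoscopic ultrasound: "The endoscopic probe will be passed into the esophagus with appropriate imaging obtained throughout the length of the esophagus". It lists no eligibility step.
- **7.3.3 (ablation)** sets the interval: "Subjects will undergo the RF ablation procedure within 30 days of randomization unless there is a medically valid reason to delay the procedure". It lists no eligibility step before the procedure.
- **7.3.4 (12 days, plus or minus 4, after the procedure)** lists "Assess study eligibility".
- **7.3.5** repeats that line at the last visit: "The final study visit will occur 3 months (+30/-30 days) after the surgery procedure".

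The exclusions in 5.2 include "Subject has esophageal bleeding prior to EnsoETM insertion", "known ingestion of acidic or caustic poisons within the prior 24 hours", pregnancy, and evidence of trauma to the esophagus. The last has no time limit. Section 5.5 lists esophageal stricture or ulceration as a ground for removal, also without saying when it must arise. The primary endpoint (4.2.1) is graded esophageal mucosal damage.

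**The concern.** The scheduled check sits on the wrong side of treatment. Criteria that describe a subject's state at or just before treatment are settled at a visit that may be a month or more earlier. The same criteria then come up for review after ablation, when an esophageal finding may be what the trial set out to measure.

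Two things are at stake. Before treatment, a subject whose status has changed since Visit 1 may reach the procedure without anyone being asked to confirm eligibility. After treatment, subjects with an injury are the ones most open to being marked ineligible. If that ended their participation, the missing later data would depend on the outcome.

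**Working it through.** The Protocol states no figure on this point to reproduce. The check sets the sections side by side and then gives a scale.

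**1. Where eligibility is assessed**

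| Section | Time | Eligibility step listed |
|---|---|---|
| 7.3.1 | Day 0 | Yes |
| 7.3.2 | Day before ablation | No |
| 7.3.3 | Ablation, up to 30 days from randomization, longer with a medical reason | No |
| 7.3.4 | Day 8 to 16 after ablation (12 ± 4) | Yes |
| 7.3.5 | 3 months ± 30 days after ablation | Yes |

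**2. Which 5.2 criteria Visit 1 can settle**

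- Caustic ingestion has a 24-hour window. An interval of 30 days is 30 × 24 = 720 hours, so an answer at Visit 1 does not cover it.
- Bleeding before insertion is by definition a state at insertion. Insertion happens in one arm only, so in controls this criterion has no stated moment.
- Pregnancy status can change over the interval.

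**3. What else happens before ablation**

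- The endoscopy (7.2.1, 7.3.2) views the whole esophagus the day before and could show bleeding, deformity or trauma.
- Section 7.1.2 calls for a history that identifies contraindications to the device. Section 2.1.2 counts caustic ingestion within 24 hours among them.
- The history has no stated timing, neither step is linked to an eligibility decision, and neither addresses pregnancy. The cover is partial.

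**4. What the follow-up check can act on**

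- Evidence of esophageal trauma has no time limit in 5.2. Section 2.2 names ulceration and hematoma among ablation injuries, and ulceration enters the endpoint scale at Grade 2a (4.2.1, Table 1). The criterion and the outcome can therefore coincide.
- Neither 7.3.4 nor 7.3.5 says which criteria are meant or what follows a failed check. The nearest consequence is the untimed entry in 5.5.

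**5. Which data are exposed**

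- The primary endpoint is read one day after ablation (7.1.1, 7.2.1), before either follow-up check.
- A removal at day 12 would lose later adverse events (secondary, 4.2.2) and 3-month rhythm (exploratory, 4.2.3).

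**6. Scale, as an upper bound**

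Inputs: N = 6 (section 1), 1:1 allocation (9.2.1), hence 3 per arm if balanced; lesion incidence p of 3% to 60% (2.2). Assume independent subjects and one rate in both arms.

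- Expected number with any lesion, 6p: 6 × 0.03 = 0.18; 6 × 0.60 = 3.6.
- Chance of at least one among 6, 1 − (1 − p)^6: 1 − 0.97^6 = 16.7%; 1 − 0.40^6 = 99.6%.
- Chance of at least one in an arm of 3, 1 − (1 − p)^3: 1 − 0.97^3 = 8.7%; 1 − 0.40^3 = 93.6%.
- At the 22% control rate of the ice-water trial described in 2.2: 1 − 0.78^3 = 52.5% for an arm of 3.

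These are chances that a lesion of any grade occurs. One subject lost from an arm of 3 takes away 1/3 of that arm's later follow-up.

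**The case against.** The strongest reply is that the follow-up line is loosely worded and carries no force. Section 5.1 frames the criteria as conditions for enrolment, nothing says 5.2 is reapplied after treatment, and failing 5.2 later is on neither the withdrawal list (5.4.1) nor the removal list (5.5). The line may only mean suitability to continue. This largely stands: a removal through this check is a risk created by the wording, not a rule the Protocol states. It does not remove the point, because the line says eligibility, the only eligibility criteria are those in 5.1 and 5.2, and 5.5 is at hand as a consequence for ulceration.

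A reader might also infer any of three stronger claims.

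- *New dysphagia after ablation would make a subject ineligible.* The text does not support this. The criterion reads "previous swallowing disorders or dysphagia, achalasia, known ingestion of acidic or caustic poisons within the prior 24 hours", and the word previous places it before the study.
- *Subjects reach treatment with no safeguard.* The endoscopy and the contraindication history contradict this, and 7.1.2 also has the oropharynx examined before placement. What is missing is a scheduled decision that uses this information and covers the remaining criteria.
- *The 16.7% to 99.6% range is the chance that someone fails the check.* It is not. Grade 1 edema need not count as trauma, and 5.5 names only stricture and ulceration.

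**Conclusion.** The point holds and is minor. An eligibility step is misplaced: it is absent between Visit 1 and ablation and present at two visits where it can serve no enrolment purpose. The pre-treatment gap is partly covered by procedures already planned. The post-treatment wording, read with 5.5, invites outcome-dependent loss of adverse-event and rhythm follow-up.

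It would go too far to conclude that the primary comparison is biased. The day-1 reading comes before both checks, so it is affected only if removed subjects are also left out of the analysis. This document does not settle that; 9.1 defers the analysis plan.

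The number of subjects exposed lies somewhere below 0.18 to 3.6 of 6. That bound assumes independence, a common rate in both arms and the full cited range, so it is too wide to say more than that a single loss would matter in arms of 3. The 3-month check adds little further risk, because adverse events and rhythm are assessed at that same visit.

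**What to change.** - Delete the eligibility line from 7.3.4 and 7.3.5.
- List an eligibility confirmation at Visit 2 (7.3.2), and a brief confirmation of the time-dependent criteria before the procedure in 7.3.3. Apply both in the two arms alike, so that the bleeding criterion has a defined moment in controls.
- State in 5.2 that the criteria are not applied to findings arising after ablation. Such findings are recorded as endpoint or adverse-event data, with follow-up continuing to 3 months.
- Reconcile 5.5 with this, since its stricture and ulceration entry has no time limit and overlaps the primary endpoint.

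The cost is Protocol and case report form wording. The confirmations use visits and procedures already planned, and the sample size is unchanged.

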### **7.3.5. Final Study Visit (Visit 4)**

The final study visit will occur 3 months (+30/-30 days) after the surgery procedure.

- Review medical history and medications history
- Record vital signs
- Adverse event assessment
- PVI Efficacy as assessed through placement of an event monitor
- Assess study eligibility

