#### **3.2. Secondary Objectives**

The secondary objective of this study is to assess the safety of the EnsoETM and efficacy of ablation when the EnsoETM is used to regulate temperature.

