**4.2.3. Exploratory Endpoints**

- Efficacy of PVI by evaluation of rhythm at 3 months following the procedure.
  - This endpoint was chosen as a precursor to future larger studies that may focus on efficacy to ensure that PVI with EnsoETM is non-inferior to PVI with LET.
- Does the use of an EnsoETM prolong or shorten the overall ablation time?

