### 9.2. Measures to Minimize Bias

#### 9.2.1. Enrollment / Randomization / Masking Procedures

Patients will be randomly assigned on a 1:1 ratio (ECD during RF ablation:No ECD device during RF ablation) one of two study groups. A random permuted block will be generated to decide the randomization assignments. The rationale for the use of random permuted block assignment is to ensure a 1:1 group assignment ratio.

To minimize bias, the individual who evaluates the radiographic imaging will be blinded to the study hypotheses and subject's group assignment, so as not to influence his/her evaluation of the condition of the subjects' esophagus. It is not possible to blind the PI, as he will be performing the procedure. Further, the patient will be blinded to the study group to which he or she was assigned. Study subjects will be debriefed regarding his or her study assignment at the final study visit. The informed consent form will explain this process to subjects. The rationale for blinding subjects to their study group assignment is to minimize the influence of the Placebo Effect.

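### The event monitor for the 3-month rhythm endpoint is placed at the last scheduled visit, where subjects also learn their arm

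*Protocol*

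**What the plan says.** Section 4.2.3 names the exploratory endpoint as "Efficacy of PVI by evaluation of rhythm at 3 months following the procedure". Section 7.3.5 fixes the timing, "The final study visit will occur 3 months (+30/-30 days) after the surgery procedure", and gives the measurement as "PVI Efficacy as assessed through placement of an event monitor".

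The only follow-up visit before that is in Section 7.3.4: "The first follow-up visit will occur 12 days (+4/-4) days after the surgery procedure". Its task list has no monitor. Neither do the lists for screening (7.3.1), the pre-procedure endoscopy (7.3.2) or the procedure visit (7.3.3). After the final visit the schedule has only unscheduled visits (7.3.6), whose one study task is an adverse event assessment.

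On masking, Section 9.2.1 says "Further, the patient will be blinded to the study group to which he or she was assigned", gives control of the placebo effect as the reason, and then states "Study subjects will be debriefed regarding his or her study assignment at the final study visit". It also says that the investigator performing the ablation cannot be blinded.

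**The concern.** A monitor records only once it is in place. If it is first placed at the last scheduled contact, the rhythm data come in after that contact, and the protocol names no wear time, return step or read-out. Because the debrief belongs to the same visit, the subject knows the arm for most or all of the recording.

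At stake is the only endpoint that addresses ablation efficacy. The protocol gives its own reasons to measure it well. Section 4.2.3 presents it as groundwork for later non-inferiority studies, and Section 2.2 reports modelling in which esophageal cooling could make a transmural atrial lesion less likely. Visit timing and the moment of unblinding are protocol matters, and a later statistical analysis plan cannot supply a missing contact or restore blinding.

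**Working it through.** The protocol gives no figure to reproduce. The check sets the schedule against the endpoint definition and the masking text, and then works out the possible recording dates.

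**Order of events** (days from the procedure, taking 3 months as 90 days)

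| Event | Section | Day | Monitor listed? |
|---|---|---|---|
| Screening; endoscopy and TEE | 7.3.1, 7.3.2 | before 0 | no |
| Ablation; repeat endoscopy | 7.3.3 | 0; 1 | no |
| First follow-up | 7.3.4 | 12 ± 4, so 8 to 16 | no |
| Final visit, with debrief (9.2.1) | 7.3.5 | 90 ± 30, so 60 to 120 | yes, placement |
| Any later scheduled contact | none | none | none |

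The protocol does not say whether placement or debriefing comes first within the final visit. If the debrief is first, the whole recording is unblinded. If placement is first, only the remainder of that visit is recorded blinded. In both cases the recording continues past the visit.

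**Recording dates.** End of recording = visit day + wear time. Wear time is not stated, so 14 to 28 days is an assumption.

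| Final visit on | End, 14 days' wear | End, 28 days' wear |
|---|---|---|
| day 60 | 60 + 14 = 74 | 60 + 28 = 88 |
| day 90 | 90 + 14 = 104 | 90 + 28 = 118 |
| day 120 | 120 + 14 = 134 | 120 + 28 = 148 |

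An early visit gives a recording that ends before day 90. A visit on day 90 gives one that ends inside the 120-day limit. The recording passes day 120 only if the visit is later than day 106 (120 − 14) or day 92 (120 − 28).

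**Number affected.** Section 1 plans six subjects, randomized 1:1. The schedule is the same for everyone, so all six readings are affected, in both arms alike.

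**The case against.** The best defence is that the wording in 7.3.5 is loose. It may mean that efficacy is judged at the final visit from a monitor already worn. That is conceivable, but no section provides for earlier placement, and if it is the intent, one sentence would say so.

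Three stronger readings are tempting, and the documents do not support them.

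- A reader might infer that the data are necessarily collected after 3 months. The dates above show otherwise: under the assumed wear times an early visit yields a recording that ends before day 90.
- A reader might infer that the efficacy data will be missing. The protocol omits a return and read-out step, but the study lasts one year (Section 1) and source data include hospital records and office charts (Section 10). The recording could be retrieved; the protocol simply does not say how.
- A reader might infer that unblinding the subject seriously biases the endpoint. Blinding is justified by the placebo effect, while the endpoint is recorded rhythm, and the operator knows the arm throughout. Bias would have to act through wear compliance, patient-triggered recordings or symptom reports, and the monitor type is not given.

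It is also fair to say that six subjects, about three per arm, cannot carry a comparative efficacy conclusion however the monitor is timed. That limits the weight of the point. It does not remove the conflict between the schedule and the endpoint, which is stated in the text and is more than a missing detail.

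**Conclusion.** The point holds in a limited form. On the plain reading of 7.3.5 and 9.2.1, the rhythm recording for all six subjects accrues after the last scheduled contact and largely or wholly after the subject has been told the arm. This rests on two things: that 7.3.5 means what it says about placement, and that a monitor records only once placed. It does not depend on the wear time. The end dates of about day 74 to day 148 do depend on it, through the assumed 14 to 28 days and a 90-day reading of 3 months.

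The main consequence is that rhythm at 3 months has no defined recording window and no point within scheduled follow-up at which the recording is complete. The risk of bias from unblinding is secondary and modest. The primary endpoint, endoscopy one day after the procedure, is unaffected. The change is still worth making, because it costs almost nothing.

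A separate and minor point: Section 3.2 makes "efficacy of ablation when the EnsoETM is used to regulate temperature" part of the secondary objective, while the matching endpoint in 4.2.3 is exploratory. The levels should be aligned, but this has no bearing on the timing problem.

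**What to change.** - **Section 9.2.1:** debrief each subject only after that subject's rhythm recording is complete and has been read.
- **Section 7.3.5:** state the wear time and a recording window anchored on 3 months after the procedure. Then either issue the monitor before the final visit so that it is returned there, or keep placement at the visit and add a return and read-out contact afterwards, for example by mail.

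Moving the monitor earlier without fixing the window would not be enough. If recording had to finish by a final visit on day 60, 28 days of wear would cover days 32 to 60 and 14 days would cover days 46 to 60, both well short of 3 months. If the monitor is to be returned at the final visit, that visit has to be timed to suit the recording window.

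The cost is a schedule amendment and either a somewhat later debrief or one additional remote contact per subject. No further subjects or tests are needed. Any statement to subjects about when they will learn their assignment, which 9.2.1 places in the consent form, would have to match.

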#### **7.3.6. Unscheduled Visit**

In addition to standard care provided during unscheduled visits, an adverse event assessment will be performed to determine whether an adverse event is present. Any adverse events will be recorded on the AE case report form.

### **7.4. Concomitant Medications, Treatments, and Procedures**

All concomitant prescription medications taken during study participation will be recorded on the case report forms. For this protocol, a prescription medication is defined as a medication that can be prescribed only by a properly authorized/licensed clinician. Medications to be reported in the CRF are concomitant prescription medications, over-the-counter medications, and non-prescription medications.

### **7.5. Rescue Medications, Treatments, and Procedures**

- If evidence of bleeding with placement of the ECD then the device will be removed.
- Surgical exploration and repair of esophageal fistula.
- Hemodynamic support including (Advanced Cardiovascular Life Support (ACLS) protocol will be implemented as needed.

## **8. Safety Assessment**

### **8.1. Specification of Safety Parameters**

#### **8.1.1. Definition of Adverse Events (AE)**

Adverse event means any untoward medical occurrence associated with the use of an intervention in humans, whether or not considered intervention-related (21 CFR 312.32 (a)).

#### **8.1.2. Definition of Serious Adverse Events (SAE)**

An AE is considered *serious* if, in the view of the PI, it results in any of the following outcomes:

- Death
- Life-threatening adverse event
- Inpatient hospitalization or prolongation of existing hospitalization

- Persistent or significant incapacity or substantial disruption of the ability to conduct normal life function
- Congenital anomaly/birth defect

Important medical events that may not fall under one of these categories may be considered serious when, based on upon appropriate medical judgment, they may jeopardize the patient or subject and may require medical or surgical intervention to prevent one of the outcomes listed in this definition.

